#### 4. Objectives and Endpoints

The primary objective is to evaluate the efficacy, as measured by improvement in MADRS total score, at 1 day post initial oral dose of AGN-241751 compared with placebo in participants with MDD. The key secondary objective is to evaluate the efficacy at Week 3 of AGN-241751 administered orally once a week compared with placebo in participants with MDD.

Objectives	Endpoints
Primary	

 
To evaluate the efficacy at 1 day post initial oral dose of AGN-241751 compared with placebo in participants with MDD
 
	
 
Change from baseline in MADRS total score at 1 day after first dose
 

Key Secondary	

 
To evaluate the efficacy at Week 3 of AGN-241751 administered orally once a week compared with placebo in participants with MDD
 
	
 
Change from baseline in MADRS total score at Week 3
 

Additional	

 
Additional endpoints to be explored to determine differences between AGN-241751 vs. placebo
 
	
 
Change from baseline in MADRS total score at 4 hours post dose, and on Study Days 5, 8, 9, 12, and 15
 
Change from baseline in Clinical Global Impressions-Severity (CGI-S) at 4 hours post dose, and on Study Days 2, 5, 8, 9, 12, 15, and 22
 
Rate of sustained responders during treatment
 
Rate of responders at 4 hours post dose, and on Study Days 2, 5, 8, 9, 12, 15, and 22
 
Rate of sustained remitters during treatment
 
Rate of remitters at 4 hours post dose, and on Study Days 2, 5, 8, 9, 12, 15, and 22
 
Time to first response
 
Time to first sustained response
 
Time to first remission
 
Time to first sustained remission
 

Objectives	Endpoints
Safety Measures	

• Adverse event (AE) recording, clinical laboratory measures, vital sign parameters, electrocardiograms (ECGs), and physical examinations

• Measure of psychotomimetic effects: Brief Psychiatric Rating Scale Positive Symptoms subscale (BPRS+)

• Measure of dissociative effects: Clinician Administered Dissociative States Scale (CADSS)

• Measure of suicidality: Columbia-Suicide Severity Rating Scale (C-SSRS)

• Measure of cognition/psychomotor function: Symbol Digit Coding (SDC)

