## 6. Study Population

### 6.1. Inclusion Criteria

Participants are eligible to be included in the study only if all of the following criteria apply:

1. Written informed consent from the participant has been obtained prior to any study-related procedures (as described in [Appendix 3](#)).
2. Male or female participants must be 18 to 65 years of age, inclusive, at the time of signing the informed consent.
3. Meet *Diagnostic and Statistical Manual of Mental Disorders*, 5th Edition (DSM-5) criteria for MDD (based on confirmation from the modified Structured Clinical Interview for DSM disorders [SCID]), with a current major depressive episode of at least 8 weeks and not exceeding 18 months in duration at Visit 1.
4. Have a minimum score of 26 on the rater-administered MADRS and a minimum score of 24 on the computer-administered MADRS at both Visit 1 (Screening) and Visit 2 (Baseline).
5. Have a difference of no greater than 7 points between the rater-administered MADRS and computer-administered MADRS at both Visit 1 (Screening) and Visit 2 (Baseline).
6. Have a CGI-S score  $\geq 4$  at both Visit 1 (Screening) and Visit 2 (Baseline).
7. Have a negative serum  $\beta$ -human chorionic gonadotropin ( $\beta$ -hCG) pregnancy test if a woman of childbearing potential (WOCBP).
8. Female participants willing to minimize the risk of becoming pregnancy for the duration of the clinical study and follow-up period. A female participant is eligible to participate if she is not pregnant, not breastfeeding, and at least one of the following conditions applies:
  - a. Not a WOCBPOR
  - b. A WOCBP who agrees to follow the contraceptive guidance in [Appendix 5](#) during the treatment period and for at least 5 terminal half-lives after the last dose of study treatment.

9. Male participants willing to minimize the risk of inducing pregnancy for the duration of the clinical study and follow-up period. A male participant must agree to use contraception as detailed in [Appendix 5](#) of this protocol during the treatment period and for at least 5 terminal half-lives after the last dose of study treatment and refrain from donating sperm during this period.
10. Able, as assessed by the investigator, and willing to follow study instructions and likely to complete all required study visits.

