**Figure 10-1 Graphical Procedure for Primary and Key Secondary Hypotheses**

### 10.3 Additional Efficacy Endpoints

Additional efficacy endpoints:

- Change from baseline in MADRS total score at 7 days after first dose of treatment
- Change from baseline in Clinical Global Impressions-Severity (CGI-S) at 1 day and 7 days after first dose of double-blind study treatment, and end of double-blind study treatment period (end of Week 3)
- Rate of MADRS sustained responders during treatment
- Rate of MADRS and CGI-S responders at 1 day and 7 days after first dose of double-blind study treatment, and end of double-blind study treatment period (end of Week 3)
- Rate of MADRS sustained remitters during treatment
- Rate of MADRS remitters at 1 day and 7 days after first dose of double-blind study treatment, and end of double-blind study treatment period (end of Week 3)
- Time to first response
- Time to first sustained response
- Time to first remission
- Time to first sustained remission

CGI-S responder is defined as patients achieving a score of  $\leq 2$  on the CGI-S of Illness scale.

During the randomized treatment period, 4 types of events for MADRS total score will be defined based on the following criteria:

- Responder:  $\geq 50\%$  reduction from baseline MADRS total score
- Sustained responder: meet responder criteria at  $\geq 2$  consecutive visits and continued through to final assessment
- Remitter: MADRS total score  $\leq 10$
- Sustained remitter: meet remitter criteria at  $\geq 2$  consecutive visits and continued through to final assessment

MADRS total score is the sum of the 10 items from the MADRS. If more than 2 items of MADRS are missing, then the total score will be set to missing.

Additional quantitative efficacy parameters will be analyzed in the following way:

Analysis of change from baseline in MADRS total score and CGI-S score will be performed using a similar MMRM for the primary and key secondary endpoints. Baseline CGI-S score will be used as a covariate for the analysis of CGI-S score. In addition, these parameters will be analyzed using ANCOVA (with LOCF imputation) as used for the analysis of primary efficacy parameters.

Additional categorical efficacy parameters will be analyzed in the following way:

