Rates for categorical parameters (response and remission) will be reported by treatment group and by visit; logistic regression model (with LOCF imputation) will be used to model the probability of a response or the probability of a remission as a function of a treatment group and the corresponding baseline score as explanatory variables.

Additional time to event efficacy parameters will be analyzed in the following way:

For the time to event type of endpoints, the log-rank test will be performed to compare the treatment arms. Kaplan-Meier curves will be plotted for each treatment arm.

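### Time to remission is tested without baseline MADRS and with no effect size for any dose; a supportive baseline-adjusted hazard model would be a cheap improvement to SAP 10.3

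*SAP*

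**What the plan says.** SAP 10.3 lists four time-to-event endpoints: first response, first sustained response, first remission and first sustained remission. The whole analysis plan for them is two sentences: "For the time to event type of endpoints, the log-rank test will be performed to compare the treatment arms" and "Kaplan-Meier curves will be plotted for each treatment arm". No stratum, covariate, hazard ratio or confidence interval is named.

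The same section defines the events. Remission is a MADRS total of 10 or less at a visit. Response is a fall of at least half from the participant's own baseline. Protocol 6.1 sets the entry floor: "Have a minimum score of 26 on the rater-administered MADRS", at both screening and baseline.

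Elsewhere the SAP's efficacy models carry the baseline score. The MMRM and the ANCOVA in SAP 10.1 do, and the by-visit logistic model for response and remission in SAP 10.3 is fitted "as a function of a treatment group and the corresponding baseline score as explanatory variables".

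Protocol Section 4 places all four time-to-event endpoints under "Additional endpoints to be explored to determine differences between AGN-241751 vs. placebo". They lie outside the graphical multiplicity procedure in SAP 10.2, which covers only the Day 2 and Week 3 MADRS comparisons.

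**The concern.** Because the remission cut-off is fixed, a participant who enters with a high score has further to go than one who enters near the floor. Baseline MADRS is therefore likely to be prognostic for time to remission. An unadjusted test leaves that variation in the comparison. With about 50 participants per arm and no stratification factor named in Protocol 7.3, some chance difference in baseline severity between a dose and placebo is to be expected. All four doses also share one placebo arm, so an imbalance there moves all four contrasts together.

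The second gap is estimation. Protocol 10.1.3 describes the study as one meant to inform Phase 3 doses, and Protocol 3.3 presents rapid onset as an expected benefit. A log-rank test returns a p-value, and Kaplan-Meier curves return a picture. Neither states how much sooner remission comes on a given dose than on placebo, or how precisely that is known.

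**Working it through.** The plan gives no power, event rate or hazard ratio for these endpoints, so there is no figure to reproduce. SAP 14 says the sample size was not based on power.

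**Step 1. Distance to the threshold (from the SAP definitions and the entry floor).** Fall for remission = baseline − 10. Fall for response = baseline ÷ 2.

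| Baseline MADRS | Fall for remission | As % of baseline | Fall for response |
|---|---|---|---|
| 26 | 16 | 62% | 13 (50%) |
| 30 | 20 | 67% | 15 (50%) |
| 35 | 25 | 71% | 17.5 (50%) |
| 40 | 30 | 75% | 20 (50%) |

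The remission target gets harder in both absolute and relative terms as baseline rises. The response target scales with baseline, so the argument does not carry over to it.

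**Step 2. Power, by simulation of one dose against placebo.** From the documents: 50 per arm, two-sided 5% level, 8 post-baseline MADRS times (4 hours; Days 2, 5, 8, 9, 12, 15 and 22). Everything else is assumed.

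*Simulation A* (800 trials per setting): baseline at least 26, mean 31, SD 3.3; change-score SDs 5.5 to 10; drug effect 4.5 points. Power for time to remission:

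| Assumed regression slope | Log-rank | Baseline-adjusted | Gain (points) |
|---|---|---|---|
| 0 | 47% | 51% | 4 |
| 0.3 | 52% | 54% | 2 |
| 0.5 | 57% | 57% | 0 |

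For time to response the change was about −1 to +2 points.

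*Simulation B* (1,500 trials per setting): baseline = 28 plus a half-normal term with scale 4 (narrow) or 8 (wide). The half-normal SD is scale × √(1 − 2/π) = scale × 0.603, that is about 2.4 or 4.8 points. Other assumptions: change SD rising from about half of 9 to 9 points by Day 22, within-participant correlation 0.8, placebo improvement 12 points by Day 22, drug effect 0 or 5 points, no dropout. Rejection rates:

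| Endpoint, spread | Effect | Log-rank | Log-rank stratified at median baseline | Cox with baseline |
|---|---|---|---|---|
| Remission, narrow | 0 | 3.7% | 4.0% | 3.4% |
| Remission, wide | 0 | 6.0% | 5.6% | 4.5% |
| Remission, narrow | 5 | 64.1% | 64.7% | 64.7% |
| Remission, wide | 5 | 49.6% | 52.9% | 52.3% |
| Response, narrow | 0 | 5.1% | 4.9% | 4.8% |
| Response, wide | 0 | 4.7% | 4.7% | 5.0% |
| Response, narrow | 5 | 80.1% | 80.6% | 80.5% |
| Response, wide | 5 | 75.3% | 76.4% | 77.2% |

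Monte Carlo standard errors: √(0.5 × 0.5 / 800) = 1.8 points for a power near 50% in A; √(0.25 / 1,500) = 1.3 points in B; √(0.05 × 0.95 / 1,500) = 0.6 points for the null rows. The null rates show no systematic inflation.

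**Step 3. Effect of a chance imbalance on the remission hazard ratio.** With the assumed SD of 3.3, the standard error of the difference in baseline means is 3.3 × √(2/50) = 0.66 points, or 0.2 SD. In the null runs of simulation A the baseline hazard ratio per SD was 0.57, 0.68 and 0.76 at slopes 0, 0.3 and 0.5. An imbalance of one standard error therefore multiplies the unadjusted hazard ratio by:

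- 0.57^0.2 = 0.89
- 0.68^0.2 = 0.93
- 0.76^0.2 = 0.95

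That is a shift of about 5 to 11%.

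**Step 4. How often this happens.** Four contrasts sharing one placebo arm of equal size have pairwise correlation 0.5. The chance that at least one exceeds one standard error is 1 − ∫ φ(p)[Φ(√2 + p) − Φ(−√2 + p)]⁴ dp = 0.71. An imbalance of that size somewhere among the four doses is the usual case.

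**The case against.** The strongest reply is that nothing here is wrong. Under randomisation the log-rank test holds its level, chance imbalance is already inside that level, and the null rows above bear this out. The endpoints are exploratory, outside the multiplicity procedure, in a trial not sized on power. The power gain is small and vanishes at the strongest assumed regression to the mean. A Cox model adds a proportional hazards assumption over eight discrete assessment times spanning three weekly doses. SAP 10.3 also states no censoring rule, so a hazard ratio would be no better defined than the present test until one is given. All of that stands. It limits the point to an improvement; it does not supply the missing estimate.

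A reader might infer four stronger things that the documents do not support:

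- **That the SAP contradicts itself**, since its logistic model adjusts for baseline. The logistic model takes status at each visit with LOCF; the log-rank test takes time to first or first sustained event. An adjusted model and an unadjusted rank test can be planned side by side.
- **That the trial yields no per-dose information on onset.** The primary endpoint is the MADRS change one day after the first dose, compared with placebo for each dose in a baseline-adjusted MMRM (SAP 10.1 and 10.2, Protocol 10.1.4). What is missing is a per-dose effect size on the time-to-event endpoints.
- **That one global five-arm test is planned.** SAP 10.3 refers only to comparing the arms. The objective in Protocol Section 4 is drug against placebo, so pairwise tests fit the text equally well.
- **That time to response suffers in the same way.** Its threshold is relative to baseline, and the simulations show little or no gain from adjustment.

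**Conclusion.** The point holds in a limited form and is a minor, optional improvement. For the two remission endpoints, the planned analysis ignores a covariate that sets the distance to the event, and it produces no effect size for any dose. Validity is not in question. The cost is about 0 to 4 percentage points of power, a remission comparison that moves by about 5 to 11% on the hazard ratio scale for a one-standard-error baseline imbalance, and no per-dose estimate with a confidence interval.

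The distance-to-threshold arithmetic and the missing estimate follow from the documents alone. The power and imbalance figures rest on an assumed baseline spread, change-score variability, treatment effect and regression to the mean; the documents give none of these. The missing per-dose estimate is the better reason to act, since it does not depend on those assumptions.

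**What to change.** Keep the log-rank test and the Kaplan-Meier curves. Add one sentence to SAP 10.3: time to first remission and time to first sustained remission will also be analysed with a proportional hazards model (Efron handling of ties, or a complementary log-log model on the scheduled assessment times) containing treatment group and baseline MADRS total score, with a hazard ratio and 95% confidence interval for each dose against placebo. The model should use the same event and censoring definitions as the log-rank test.

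The same model may be reported for the two response endpoints to obtain hazard ratios, but no power gain should be expected there.

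The cost is that sentence and the matching output; no new data are needed. The one downside is reliance on proportional hazards, the setting in which the log-rank test itself works best.

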## 11 Safety Analyses

The safety analysis will be performed using the Safety Population. The safety parameters will include adverse events (AEs), clinical laboratory, vital sign, electrocardiographic (ECG), BPRS+, CADSS, C-SSRS, and SDC parameters. For each safety parameter, except AEs, the last nonmissing safety assessment before the first dose of double-blind study treatment will be used as the baseline for all analyses of that safety parameter. Continuous variables will be summarized by number of participants and mean, SD, median, minimum, and maximum values. Categorical variables will be summarized by number and percentage of participants.

## 11.1 Adverse Events

Adverse events will be coded by system organ class and preferred term using the Medical Dictionary for Regulatory Activities (MedDRA), version 21.0 or newer.

An AE will be considered a treatment-emergent adverse event (TEAE) if the AE began or worsened (increased in severity or became serious) on or after the date of the first dose of double-blind study treatment. However, an AE that occurs more than 30 days after the last dose of double-blind study treatment will not be counted as a TEAE. Per case report form instructions, a new AE record will be created for any AE that worsens; therefore TEAEs can be identified as those AEs with recorded onset date on or after the date of the first dose of double-blind study treatment and within 30 days after the last dose of double-blind study treatment. For participants who enter the double-blind treatment period, but did not enter the safety follow-up period, any AE that occurred up to 30 days after the date of the last dose of double-blind study treatment, is considered as TEAEs for the double-blind treatment period. For participants who entered the safety follow-up period, AEs that occurred on or after the date of Visit 9/ET will be considered as TEAEs for the safety follow-up period.

An AE will be considered a treatment-emergent serious AE (TESAE) if it is a TEAE that additionally meets any SAE criteria.

Summaries of TEAEs/AEs will be presented separately for the double-blind treatment period and safety follow-up period.

The number and percentage of participants reporting TEAEs in each treatment group will be tabulated by system organ class and preferred term. In addition, the number and percentage of participants reporting TEAEs in each treatment group will be tabulated by system organ class, preferred term, and severity for the double-blind treatment period. The number and percentage of participants reporting treatment related TEAEs in each treatment group will be tabulated by system organ class and preferred term for the double-blind treatment period.

If more than 1 AE is coded to the same preferred term for the same participant, the participant will be counted only once for that preferred term using the most severe for the summarizations by severity.

Listings of SAEs and AEs leading to discontinuation by participant will be presented.

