### **8.1. Discontinuation of Study Treatment**

All randomized participants who prematurely discontinue from the study, regardless of cause, should be seen for a final assessment at an ET Visit. A final assessment will be defined as completion of the evaluations scheduled for all participants at Visit 9/ET Visit. Participants who prematurely discontinue from the study before completing 3 weeks of double-blind treatment should enter the 1-week safety follow-up period.

Any participant may be withdrawn due to AE at the discretion of the investigator.

Any participant who meets any of the following criteria at any point during the study must be withdrawn from participation, due to AE(s) related to suicide:

- a) A suicide attempt
- b) Significant risk, as judged by the investigator, based on the psychiatric interview or information collected in the C-SSRS
- c) MADRS Item 10 score  $\geq 5$

In the event that a participant is withdrawn for a suicide-related AE, the participant should be referred for additional treatment or hospitalization, as clinically indicated, in addition to withdrawing the participant from the study.

Discontinuation of study treatment for abnormal liver function (criteria for potential Hy's law described in Section 9.2.6) should be considered by the investigator if the investigator believes that it is in best interest of the participant.

If a clinically significant finding is identified after enrollment, the investigator or qualified designee will determine if the participant can continue in the study and if any change in participant management is needed. Any new clinically relevant finding should be reported as an AE.

See the schedule of activities (Section 2) for data to be collected at the early termination visit and the safety follow-up visit.

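### SAP 11.1 places adverse events dated to Visit 9/ET in follow-up, though the SAP otherwise treats that visit as double-blind, and its double-blind counting window depends on whether follow-up is entered

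*SAP*

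**What the plan says.** SAP 11.1 sets the boundary between the two periods in two ways. For participants who entered safety follow-up, "AEs that occurred on or after the date of Visit 9/ET will be considered as TEAEs for the safety follow-up period". For participants treated in the double-blind period who did not enter follow-up, "any AE that occurred up to 30 days after the date of the last dose of double-blind study treatment, is considered as TEAEs" of the double-blind period.

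The boundary decides which table an event enters: "Summaries of TEAEs/AEs will be presented separately for the double-blind treatment period and safety follow-up period". Incidence by system organ class and preferred term is planned for both periods. The severity table is by system organ class, "preferred term, and severity for the double-blind treatment period". The relatedness table is restricted in the same way: "treatment related TEAEs in each treatment group will be tabulated by system organ class and preferred term for the double-blind treatment period". Outside the tables, "Listings of SAEs and AEs leading to discontinuation by participant will be presented", with no limit to a period.

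Other sections treat Visit 9/ET differently:

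- SAP Table 5-1 shows it as the last visit of the double-blind period.
- SAP Table 16-1 includes the final double-blind or ET visit in the Week 3 window.
- SAP 11.2 tabulates potentially clinically significant (PCS) laboratory values for the double-blind period.
- SAP 11.4 plans an ECG shift table from baseline to the end of the double-blind period.
- Scheduled safety laboratory tests, ECG and physical examination take place only at screening and at Visit 9/ET (SAP Table 5-1; Protocol 9.4.1, 9.4.3 and Appendix 2).

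Protocol 10.4.2.1 defines treatment-emergent events with one 30-day limit after the last dose and no division at Visit 9/ET.

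**The concern.** The scheduled postbaseline laboratory, ECG and physical examination data come from one visit. Under SAP 11.2, a laboratory value from that visit is a double-blind finding. Under SAP 11.1, an AE recorded because of the same value and dated to that visit is a follow-up event. The same applies to an AE that starts on the day of early termination in someone who then enters follow-up. Such events are absent from the double-blind incidence table and from the only severity and relatedness tables planned.

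The second difficulty is that the length of the double-blind counting window is settled by attendance after treatment. Attendance is determined after randomization and could be related to treatment, so it is a poor basis for deciding which table an event enters. At stake are the by-dose safety tables of a study that Protocol 10.1.3 says is meant to inform Phase 3 doses.

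**Working it through.** The plan states no figure to reproduce, so the check is a day count.

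**Inputs**

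- Double-blind doses on Days 1, 8 and 15 (SAP section 4).
- Visit 9 on Day 22, with a tolerance of 2 days either way (SAP Table 5-1).
- The two period rules in SAP 11.1.
- About 50 participants per arm (SAP section 14).

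**Formulas**

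- Enters follow-up: double-blind window = Day 1 to (Visit 9/ET day − 1).
- Does not enter follow-up: double-blind window = Day 1 to (last dose day + 30).

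| Case | Enters follow-up | Does not enter |
|---|---|---|
| Three doses, Visit 9 on Day 22 | Days 1–21 (22 − 1) | Days 1–45 (15 + 30) |
| Three doses, Visit 9 on Day 20 or Day 24 | Days 1–19 or Days 1–23 | Days 1–45 |
| Two doses, ET on Day 8 (dosing day) | Days 1–7 (8 − 1) | Days 1–38 (8 + 30) |
| One dose, ET on Day 5 | Days 1–4 (5 − 1) | Days 1–31 (1 + 30) |

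For three-dose participants the difference is 45 − 21 = 24 days, a ratio of 45/21 = 2.1. In the Day 8 case, which assumes that dosing and the ET evaluations fall on one date, even the day of the second dose lies outside the double-blind window.

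**Where an AE with onset on the Visit 9/ET date goes, for a participant who enters follow-up**

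| Output | Included? |
|---|---|
| Double-blind incidence table | No |
| Severity table | No (double-blind only) |
| Treatment-related table | No (double-blind only) |
| Follow-up incidence table | Yes |
| Listings | Yes, if serious or leading to discontinuation |

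An AE with onset before the visit date stays in the double-blind tables, whatever it later leads to.

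**Scale.** One participant moved in an arm of 50 changes that arm's incidence by 1/50 = 2 percentage points. This is the size of one move. The documents do not say how many to expect.

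**With the Visit 9/ET date counted as double-blind.** The three-dose participant seen on Day 22 has Days 1–22 as double-blind and Days 23–45 as follow-up. In a uniform window, participants with three doses are counted over Days 1–45 whether or not they enter follow-up.

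**The case against.** The strongest reply is that no event is lost. Events moved by the rule remain treatment-emergent, appear in the follow-up incidence table, and are listed if serious or leading to discontinuation. The AE tables are descriptive with no test planned, and Protocol 10.4.2 leaves the detail of the safety analysis to the SAP, so splitting the periods is not in itself a departure from the protocol. The rule for those who skip follow-up is a sensible catch-all, because without it their late events would enter no table. All of this stands and keeps the point modest. It does not explain why the Visit 9/ET date is double-blind for laboratory values and follow-up for AEs, nor does it supply a severity or relatedness table for the moved events.

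Four stronger readings are tempting, and the documents do not support them.

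- *AEs that cause withdrawal vanish from the double-blind tables.* Only those with onset on or after the ET date move, and only in participants who enter follow-up.
- *Suicide-risk withdrawals are moved systematically.* Protocol 8.1 says that such participants "must be withdrawn from participation, due to AE(s) related to suicide", but not that the triggering visit becomes the ET visit. The MADRS and C-SSRS look back to the previous assessment, so onset may be dated earlier. SAP 11.5.4 also summarizes suicidal ideation and behavior by arm and lists the AEs of affected participants.
- *Day 45 against Day 21 is a difference in observed time.* It is a counting window. People who skip follow-up have no scheduled contact, and Protocol 9.2.1 does not oblige investigators to seek events in former participants.
- *The comparison with placebo is distorted.* The documents give no count of early terminations, same-day onsets or people who skip follow-up. Early discontinuers are told to enter follow-up, so the last group may be small. SAP 11.1 does not define what counts as entering.

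**Conclusion.** The point holds as an inconsistency in period assignment that should be corrected. For participants who enter follow-up, AEs dated to Visit 9/ET are placed against the SAP's own schedule, visit windows and laboratory tabulation, and they receive no severity or relatedness summary. The double-blind window also differs by attendance: nominally 21 against 45 days for three doses, with the first figure ranging from 19 to 23 under the visit tolerance.

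This rests on the nominal dose days and on the assumption that some AEs will have onset dated to Visit 9/ET. That is plausible for findings first seen in that visit's laboratory tests, ECG or physical examination, but the documents do not quantify it. The number affected is unknown and may be small. No direction or amount of bias between arms is claimed.

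**What to change.** Make two changes in SAP 11.1.

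1. For participants who enter follow-up, count AEs with onset up to and including the Visit 9/ET date as double-blind, and only AEs with later onset as follow-up. This brings the AE rule into line with Tables 5-1 and 16-1 and with the laboratory tabulation.
2. Add incidence, severity and treatment-related tables for all participants over one window, from the first double-blind dose to 30 days after the last. SAP 11.2 already uses this window for Hy's law, and Protocol 10.4.2.1 sets the same 30-day limit. These tables do not depend on whether follow-up was entered, so the catch-all for those who skip it can stay in the by-period tables.

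The cost is SAP wording and one extra set of tables. No new data are needed.
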